11.3.5 RTOG CNS toxicity determination

Neurologic/brain toxicity assessment will be made during treatment and at each follow up (1 month, 3 months, and every 3 months thereafter) (See **Appendix B** for definitions).

11.3.6 Adverse Events (AEs)

Any unfavorable and unintended sign, symptom, or disease temporally associated with the use of a medical treatment or procedure regardless of whether it is considered related to the medical treatment or procedure (attribution of unrelated, unlikely, possible, probable, or definite). These events will be recorded for each subject and is subject to review by the investigators and data safety monitoring committee (DSMC).

11.3.7 Serious Adverse Events (SAEs)

Any adverse event that results with any of the following outcomes:

- Death;
- A life-threatening experience;
- Inpatient hospitalization or prolongation of existing hospitalization;
- A persistent or significant disability/incapacity;
- A congenital anomaly/birth defect; or
- Other medically important events.

Important medical events that may not result in death, be life threatening, or require hospitalization may be considered an SAE, when, based upon medical judgment, they may jeopardize the patient and may require medical or surgical intervention to prevent one of the outcomes listed in the definition. These events will also be recorded for each subject and is subject to review by the investigators and data safety monitoring committee (DSMC). In addition, these events will be reported to the Emory University Institutional Review Board (IRB).

11.4 Feasibility Assessment

11.4.1 Criteria of feasibility

Treatment plans using the RapidArc treatment planning software to deliver simultaneous in-field boosts to gross metastatic lesions have been successfully generated in our department. Therefore, the main question of feasibility is regarding whether the treatment setup and delivery can be accomplished in a “reasonable” period of time. A typical treatment slot for conventional radiation therapy in our department is 15 minutes. We will define 2 treatment slots, or 30 minutes as a “reasonable” time for this treatment. Therefore, this treatment will be considered feasible if the treatment setup/delivery time is <30 minutes in >90% of treatment fractions.

11.4.2 Feasibility data to be collected

Our departmental record-and-verify system will document the time when setup OBI images are first obtained and when the radiation treatment delivery is turned off for each treatment fraction. This time will be recorded for each treatment fraction. An additional 5 minutes will be added to this time to estimate the time required to setup a patient prior to the acquisition of the first OBI image plus the time from when the machine is turned off to when the patient is released from the treatment couch. This total time will need to be <30minutes for the treatment to be considered "reasonable."

12.0 DATA COLLECTION

12.1 Data Fields

The following data will be collected on each patient: name, date of birth, medical record number, tumor characteristics by pathology of surgical specimen, radiologic results, performance status, radiation and chemotherapy treatment parameters, clinical outcome including local and regional control, overall survival, treatment complications, neurocognitive assessments, and QOL assessments.

12.2 Criteria for patient to be considered off study

- 12.1.1 Local CNS disease progression.
- 12.1.2 Patient death.
- 12.1.3 Patient request to come off study.
- 12.1.4 Patient is discharged to hospice

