13.1.2 Secondary Endpoints (to be compared with standard historical controls)

- Progression-free survival
- Overall Survival
- Neurocognitive effects
- QOL outcomes

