13.2 Sample size

This will be a single cohort pilot study. Safety of the chosen dose level has been shown based on the previous phase I dose escalation iteration of this study.

18 patients will be enrolled consecutively into this single arm pilot study.

If a patient is not able to complete follow up to the toxicity assessment point of 4 months due to a toxicity judged not to be at least possibly related to therapy, then that patient will be replaced by the next patient enrolled.

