13.3 Statistical Analysis

Descriptive statistics will be performed on the clinical and treatment factors on subjects on this study. Categorical data will be presented on frequency tables while continuous data will be presented as mean, standard deviation, median and range. Local control, regional brain control, progression-free survival and overall survival will be assessed using the Kaplan-Meier method with censoring as appropriate. Univariate and multivariate analysis will be performed with these endpoints to determine patient factors that may influence outcome. These curves will also be compared to previously published results as historical controls. The results of the neurocognitive and quality of life surveys/tests will be plotted for each patient to assess for a general trend over time. The trend over time can also be analyzed by linear regression analysis. Each point in time can be compared with historical controls using a student's t-test to determine whether there is a significant difference in the survey/test scores in patients on our study versus historical results.

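### Section 12.2 takes patients off study at local CNS progression and hospice discharge without a visible rule for survival follow-up; if data collection stops there, Kaplan-Meier overall survival is biased upward

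*Combined protocol and SAP*

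**What the plan says.** Section 12.2, under the data collection heading, gives four off-study criteria. Two are death and the patient's own request. The other two are "Local CNS disease progression" and "Patient is discharged to hospice". The section does not say what, if anything, is recorded once a patient is off study.

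Section 12.1 lists the data for each patient, including "clinical outcome including local and regional control, overall survival, treatment complications". It gives no duration, no source for dates of death and no mention of patients who are off study.

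Section 13.3 says that "overall survival will be assessed using the Kaplan-Meier method with censoring as appropriate" and adds: "These curves will also be compared to previously published results as historical controls". It does not define the censoring further, and neither it nor section 13.1.2, where overall survival is a secondary endpoint, names a control study.

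Sections 11.1 to 11.3 schedule cognitive tests, quality of life, MRI and toxicity visits, but no survival contact after a patient is off study. Section 13.2 replaces a patient who is "not able to complete follow up to the toxicity assessment point of 4 months" only if this is "due to a toxicity judged not to be at least possibly related to therapy". The Appendix C timeline grid is not visible in the copy reviewed.

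**The concern.** Treatment lasts 10 fractions, so local progression and hospice discharge will mostly come after it has ended. Being off study can then hardly mean being off treatment; what is left to stop is follow-up. A data manager could reasonably read section 12.2 as the point at which data collection ends and censor the patient on that date.

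Kaplan-Meier assumes that a censored patient has the same outlook as those still at risk. Discharge to hospice is a sign that death is near, and section 1.0 says that patients with recurrent brain metastases most often die of CNS disease. Censoring at these events would remove deaths from the curve selectively. An apparent survival gain over published results could then come from the off-study rule and not from the treatment.

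**Working it through.** The plan states no figure that depends on this point, and its 18 patients carry no alpha, power or effect size, so there is nothing to reproduce. The check asks which way, and how far, the survival curve moves if follow-up ends at the off-study date.

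**Inputs from the protocol.** Median survival with treatment is about 4 months (section 1.0; this describes treated patients generally, not a cohort with KPS of at least 70). There are 18 patients (13.2), and the last scheduled cognitive and quality-of-life assessment is at 24 months (11.1.5, 11.2.2). None of the 12 earlier patients had local failure (section 1.0; length of follow-up not stated).

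**Assumptions, not in the protocol.** Survival is exponential. Hospice discharge precedes a share p of deaths, at an exponential lead time with mean L of 0.7 or 1.0 month.

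**Hospice discharge.** Let h = ln 2 / median, so h = 0.173 per month at 4 months. At time t, a fraction 1/(1 + hL) of the surviving hospice-bound patients has not yet been censored. The observed hazard is therefore

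h × (1 − p) / [(1 − p) + p/(1 + hL)],

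and the median is multiplied by

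1 + p / [(1 − p)(1 + hL)].

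For p = 30% and L = 1.0: 1 + 0.4286/1.173 = 1.365, and 4 × 1.365 = 5.46 months. Simulating 400,000 survival times per scenario gives the same picture:

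| Hospice share p | Formula, L = 0.7 / 1.0 | Simulated median, L = 0.7 / 1.0 |
|---|---|---|
| 10% | 4.40 / 4.38 | 4.40 / 4.39 |
| 20% | 4.89 / 4.85 | 4.90 / 4.86 |
| 30% | 5.53 / 5.46 | 5.53 / 5.46 |
| 50% | 7.57 / 7.41 | 7.56 / 7.42 |

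In relative terms the simulated inflation is about 10%, 22–24%, 37–41% and 86–95%. These ranges also cover true medians of 7 and 10 months, so they do not hinge on the 4-month figure. With administrative censoring at 24 months and L = 1.0, the deaths seen among 18 patients fall from 17.7 to 12.4 at p = 30%, and to 8.8 at p = 50%. If deaths after off-study are recorded, the true median of 4.0 months is recovered.

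**Local progression.** If 10% or 20% of patients are censored at local progression, at 30–90% of their survival time, a 4.0-month median reads as 4.3 or 4.7. The result depends on what follows progression. In a model with a 6-month median before progression and 15–46% of patients progressing, there is no bias if the death hazard is unchanged. If it doubles, true medians of 5.8 to 5.0 months read as about 6.0; if it triples, 5.6 to 4.6 read as about 6.0. With 0 of 12 local failures, the one-sided 95% upper limit is 1 − 0.05^(1/12) = 22%.

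**Sampling error.** With 18 deaths, an approximate 95% interval for a 4-month median has the factor exp(1.96/√18) = 1.59, giving 2.5 to 6.3 months. The 10–30% scenarios lie inside it; the 50% scenario does not.

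**Toxicity at 4 months.** At p = 50%, a 4-month median and L = 1.0, the expected number who go to hospice before 4 months and are still alive at 4 months is 18 × 0.5 × 0.5 × 0.173/(0.173 + 1) = 0.66, or at most about 0.7 of 18. The other early hospice exits die before 4 months, so no follow-up rule could complete their 4-month assessment.

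**The case against.** The strongest answer is that the harmful premise is not in the text. Section 12.2 is not a censoring rule and does not say that data collection stops. Section 12.1 lists overall survival for every patient without exception, and also records identifiers that would allow a chart search. A reader might infer that follow-up does end at off-study and that the survival estimate is therefore biased; the documents do not establish this. That part of the objection stands. It does not settle the matter, because section 12.1 gives no method or duration and section 13.3 leaves the censoring to judgement.

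Appendix C may contain a survival follow-up rule. If it does, the missing-follow-up part of the point falls away, though section 13.3 would still need a defined censoring rule.

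The direction is not automatic for local progression: it requires a higher death hazard afterwards, and section 1.0 speaks to the cause of death after recurrence, not its timing. For hospice discharge the upward direction is hard to doubt, although the protocol gives no time from discharge to death. The size is set largely by the assumed hospice share. Because no control study is named, how the controls handled follow-up cannot be checked either.

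A reader might also infer that two primary endpoints, toxicity and regional control, are seriously under-recorded. The figures do not support that. At most about 0.7 of 18 patients would be off study in hospice yet alive at 4 months. New lesions would be missed only after a local failure, and none was seen in 12 patients. The narrow replacement rule in section 13.2 is a separate matter.

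**Conclusion.** The point holds as a risk created by an incomplete rule, not as a demonstrated bias. If section 12.2 is applied as the end of data collection, overall survival is biased upward, mainly through hospice discharge. If deaths are still recorded, the survival bias is zero.

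The illustrative size, a 4-month median read as 4.4 to 5.5 months at hospice shares of 10% to 30%, rests on assumed shares, a mean lead of 0.7 to 1.0 month and exponential survival. A shift of that size is within the sampling error of 18 patients, but it is systematic and always favours the treatment.

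Overall survival is a secondary endpoint in a pilot without a formal decision rule. Feasibility, measured during the 10 fractions, is unaffected. The ambiguity is nevertheless worth removing, because the comparison with published results is planned and the remedy is cheap.

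**What to change.** Amend section 12.2 so that local progression and hospice discharge end scheduled protocol assessments only. Vital status and date of death, from the chart or by telephone, and any known late toxicity should still be recorded until death or withdrawal of consent.

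In section 13.3, state that overall survival is censored only at the last date known alive or at withdrawal of consent, never at progression or hospice discharge. Report the numbers off study by reason.

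This concerns data collection and analysis only and changes no treatment. It costs a short amendment and modest chart or telephone work in 18 patients, and the reported survival may look less favourable. If the sponsor already follows patients this way, the amendment merely writes it down.

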12.3 Data Safety Monitoring

12.3.1 Data Safety Monitoring Committee (DSMC)

We will use the Winship Cancer Institute data safety monitoring committee chaired by [name] as an independent review. As per WCI policy, the DSMC monitors all investigator initiated studies and cooperative group studies at Winship. Each qualifying study is reviewed at least once a year. Two of the first 5 patients enrolled to investigator-initiated studies and 10% of total accrual is reviewed.

Once a chart is monitored, the PI and the study coordinator are presented with the findings. They have a 2 week period to respond to the findings. A summary report is submitted to the DSMC for committee review. Any serious unanticipated problem is reported to the IRB with due notice to the PI.

Included in the review:

- Regulatory documents
- Patient eligibility
- Informed consent process
- Accuracy and timeliness of data
- Verification of source documents
- Toxicity assessment process

- Submission of SAEs

13.0 STATISTICAL CONSIDERATIONS

13.1 Study endpoints

13.1.1 Primary endpoints

- Feasibility – Measurement of the amount of time required for daily treatment
- Rates of toxicities
- Local brain control
- Regional brain control

13.1.2 Secondary Endpoints (to be compared with standard historical controls)

- Progression-free survival
- Overall Survival
- Neurocognitive effects
- QOL outcomes

13.2 Sample size

This will be a single cohort pilot study. Safety of the chosen dose level has been shown based on the previous phase I dose escalation iteration of this study.

18 patients will be enrolled consecutively into this single arm pilot study.

If a patient is not able to complete follow up to the toxicity assessment point of 4 months due to a toxicity judged not to be at least possibly related to therapy, then that patient will be replaced by the next patient enrolled.

13.3 Statistical Analysis

Descriptive statistics will be performed on the clinical and treatment factors on subjects on this study. Categorical data will be presented on frequency tables while continuous data will be presented as mean, standard deviation, median and range. Local control, regional brain control, progression-free survival and overall survival will be assessed using the Kaplan-Meier method with censoring as appropriate. Univariate and multivariate analysis will be performed with these endpoints to determine patient factors that may influence outcome. These curves will also be compared to previously published results as historical controls. The results of the neurocognitive and quality of life surveys/tests will be plotted for each patient to assess for a general trend over time. The trend over time can also be analyzed by linear regression analysis. Each point in time can be compared with historical controls using a student's t-test to determine whether there is a significant difference in the survey/test scores in patients on our study versus historical results.

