1.0 INTRODUCTION/BACKGROUND

Brain metastases are the most common adult intracranial tumor, occurring in approximately 10% to 30% of adult cancer patients, and represent an important cause of morbidity and mortality in this population.¹ The risk of developing brain metastases differs with different primary tumor histologies, with lung cancer accounting for approximately one half of all brain metastases.² The prognosis of patients with brain metastases is poor. The median survival time of untreated patients is approximately 1 month.³ With treatment, the overall median survival time after diagnosis is approximately 4 months.⁴ The RTOG recursive partitioning analysis (RPA) describes three prognostic classes, defined by age, Karnofsky Performance Score (KPS), and disease status.⁵ The most widely used treatment for patients with multiple brain metastases is WBRT. The appropriate use of WBRT can provide rapid attenuation of many neurological symptoms, improve quality of life, extend median survival, and be especially beneficial in patients whose brain metastases are surgically inaccessible or when other medical considerations preclude surgery.^{6,7} The use of adjuvant WBRT after resection or stereotactic radiosurgery (SRS) has been proven to be effective in terms of improving local control of brain metastases, and thus, the likelihood of neurological death is decreased.⁸

The majority of patients who achieve local tumor control die from progression of extracranial disease, whereas the cause of death is most often due to CNS disease in patients with recurrent brain metastases.^{7,8} Currently, no consensus on the optimal radiation schedule for patients with brain metastases is established. Standard treatment regimens include dose fractionation schemes evaluated in the early RTOG studies and range from 20 Gy in 5 fractions to 40 Gy in 20 fractions. The exact regimen used is generally at the discretion of the treating physician and often depends upon issues such as the severity of CNS symptoms, the extent of systemic disease, and physician preference.

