This previous version of this study was a phase I dose escalation trial giving 25 Gy in 10 fractions to the whole brain with simultaneous infield boost (SIB) to a total of 45 Gy in 10 fractions to gross brain metastatic disease. Prior to this, patients were enrolled onto one of two cohorts with whole brain dose of 30 Gy in 10 fractions with SIB to total of 45 Gy in 10 fractions to gross brain metastatic disease or whole brain dose of 37.5 Gy in 15 fractions with SIB to total of 52.5 Gy in 15 fractions to gross brain metastatic disease. A total of 12 patients have been previously enrolled on this trial. No patients have experienced a dose limiting toxicity (grade 3 or above) at least possibly due to study therapy. Also, no patients experienced local brain failure/progression at a site of treated metastatic brain disease. Based on this, we no longer feel that dose escalation to the gross brain disease is warranted and would proceed with a single arm pilot study treating patients with 25 Gy in 10 fractions to the whole brain with simultaneous infield boost (SIB) to a total of 45 Gy in 10 fractions to gross brain metastatic disease.

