2.0 OBJECTIVES

2.1 Primary Objectives

- 2.1.1 To determine the feasibility of treating brain metastasis patients with whole brain radiation and simultaneous focal boost using an RA technique. (see Section 11.4)
- 2.1.2 To determine the locoregional control [at visible lesion(s) and new site(s)] in the brain of patients treated with a concomitant boost RA plan.

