3.2 Exclusion Criteria

- 3.2.1 Previous whole brain radiation therapy
- 3.2.2 Previous radiosurgery to any currently progressive gross metastatic disease
- 3.2.3 Previous radiosurgery to any intracranial site within the prior 6 weeks
- 3.2.4 RPA class III (KPS < 70 , see **Appendix A**).
- 3.2.5 Radiosensitive (eg. small cell lung carcinomas, germ cell tumors, leukemias, or lymphomas) or unknown tumor histologies.
- 3.2.6 Concurrent chemotherapy (no chemotherapy starting 14 days before start of radiation)
- 3.2.7 Evidence of leptomeningeal disease by MRI and/or CSF cytology.
- 3.2.8 Current pregnancy
- 3.2.9 No metastases to brain stem, midbrain, pons, or medulla or within 7 mm of the optic apparatus (*optic nerves and chiasm*).

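### Primary local and regional control use Kaplan-Meier with no rule for death without brain failure; if those deaths are censored, the proportion of patients who fail is overstated.

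*Combined protocol and SAP*

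**What the plan says.** Section 2.1.2 sets a primary objective: "To determine the locoregional control [at visible lesion(s) and new site(s)] in the brain". Section 13.1.1 lists local brain control and regional brain control as separate primary endpoints, and section 13.1.2 lists progression-free survival and overall survival as secondary.

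Section 13.3 gives all four the same method: "Local control, regional brain control, progression-free survival and overall survival will be assessed using the Kaplan-Meier method with censoring as appropriate". It also plans univariate and multivariate analyses of these endpoints and a comparison of the curves with published results. The reference to censoring is the only handling rule.

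Section 11.3.4 defines CNS progression by growth of a tracked lesion or by a new metastasis, and does not mention death. Section 12.2 takes a patient off study at death and also at "Local CNS disease progression" and when "Patient is discharged to hospice". No analysis rule is attached to any of these.

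The background (section 1.0) expects deaths without local failure: "The majority of patients who achieve local tumor control die from progression of extracranial disease".

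**The concern.** A patient who has died cannot later fail in the brain, so death without brain failure is a competing event. The wording of section 13.3 allows two treatments of it:

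- **Deaths censored.** 1 minus Kaplan-Meier then estimates failure in a hypothetical setting without death. That exceeds the proportion of patients who fail whenever failures follow such deaths.
- **Deaths counted as failures.** The endpoint becomes a form of progression-free survival, which the plan already lists separately.

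A reader of the final report could not tell which quantity a primary control rate represents, and the comparison with published curves has the same ambiguity.

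Regional control has a further problem. Leaving the study at local progression or hospice discharge can end follow-up for new lesions, and neither is clearly unrelated to the risk of regional failure.

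**Working it through.** The plan states no target rate, precision or power for local or regional control, and the 18 patients are not derived from either endpoint. There is therefore no figure to reproduce. The check measures how far the possible treatments of death differ.

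**Inputs**

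- Sample size: 18 (section 13.2).
- Survival: the only figure for treated patients is in section 1.0: "With treatment, the overall median survival time after diagnosis is approximately 4 months". It covers treated patients overall, whereas section 3.2 excludes RPA class III. Medians of 4, 6, 9 and 12 months are therefore assumed.
- Brain failure: no rate is given for this trial. Constant hazards h of 1%, 2%, 4% and 6% per month are assumed.
- Times of 6 and 12 months are chosen for illustration, since the plan names none.
- Hazards of failure and death are assumed constant and independent.

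**Formulas**, with d = ln 2 / median survival:

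- Deaths censored: 1 − KM(t) = 1 − exp(−h·t)
- Death competing: CIF(t) = h/(h+d) × [1 − exp(−(h+d)·t)]
- Deaths as failures: 1 − exp(−(h+d)·t)
- Expected number alive and failure-free: 18 × exp(−(h+d)·t)

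**Worked case**: h = 0.02, median 12 months, t = 12.

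- d = 0.6931/12 = 0.0578, so h + d = 0.0778 and exp(−12 × 0.0778) = 0.393.
- Deaths censored: 1 − exp(−0.24) = 21.3%.
- Death competing: (0.02/0.0778) × 0.607 = 15.6%.
- Deaths as failures: 60.7%.
- At risk: 18 × 0.393 = 7.1 patients.

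**12-month failure by assumed median survival**

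| Median (months) | h = 2%: 1−KM | h = 2%: CIF | h = 6%: 1−KM | h = 6%: CIF | Ratio (1−KM)/CIF, h = 6% to 1% |
|---|---|---|---|---|---|
| 4 | 21.3% | 9.3% | 51.3% | 24.2% | 2.12 to 2.33 |
| 6 | 21.3% | 11.9% | 51.3% | 30.0% | 1.71 to 1.82 |
| 9 | 21.3% | 14.2% | 51.3% | 35.3% | 1.45 to 1.52 |
| 12 | 21.3% | 15.6% | 51.3% | 38.6% | 1.33 to 1.38 |

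At 6 months the ratios are 1.56 to 1.60, 1.36 to 1.38, 1.23 to 1.25 and 1.17 to 1.18 for medians of 4, 6, 9 and 12 months.

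Over the whole grid, counting deaths as failures gives 12-month figures of 56% to 94%, against a cumulative incidence of 5% to 39%. The expected number at risk is 4.4 to 12.0 at 6 months and 1.1 to 8.0 at 12 months.

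**Cross-check by simulation** (18 patients, 4,000 runs per scenario, failure of 20% at 12 months in the absence of death). With a 4-month median, mean 1 − KM is 20.0% against a cumulative incidence of 8.7%. With a 12-month median, it is 20.2% against 14.7%. This agrees with the formulas (20.0% against 8.7% and 14.6%).

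**Local progression as a further competing event for regional failure** (regional hazard 6%, local hazard 2%, 12 months). With hazard l for local progression, the regional incidence is r/(r+l+d) × [1 − exp(−12(r+l+d))]. For medians of 4, 6, 9 and 12 months it falls from 24.2%, 30.0%, 35.3% and 38.6% to 22.6%, 27.7%, 32.4% and 35.2%. This is a smaller effect than that of death.

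**The case against.** **The estimand.** Kaplan-Meier with deaths censored estimates a recognised quantity, failure in the absence of death. It is too high only when read as the proportion of patients who fail. That is correct, but the plan neither names that quantity nor argues that censoring at death is independent.

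**Deaths as failures is the less likely reading.** Progression is defined by imaging alone and progression-free survival is listed separately. This stands, and the 56% to 94% figures should carry little weight. It also makes censoring, the reading that overstates, the natural one.

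**The largest ratios need the 4-month median.** This also stands. With medians of 9 and 12 months the ratios are 1.17 to 1.25 at 6 months (0.9 to 5.7 points) and 1.33 to 1.52 at 12 months (3.1 to 16.0 points). Those medians are assumptions too.

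**Local control may be unaffected.** Section 1.0 reports of the 12 earlier patients that "no patients experienced local brain failure/progression at a site of treated metastatic brain disease". With no local failures and deaths censored, the two estimates agree. The statement does not cover new sites, so it gives no reassurance on regional control. Equally, the background does not say how many patients die free of new brain lesions.

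**This is a small pilot with no decision rule on control.** The only numerical success criterion is treatment time (section 11.4.1). With 18 patients the sampling error is large: an exact 95% interval for 3 of 18 is 3.6% to 41.4%. This limits the consequence but does not settle what a primary endpoint estimates.

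**Off-study need not mean follow-up stops.** Section 12.2 does not say that imaging or vital status ceases to be collected. That is fair, and the plan should state it.

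**Published curves may themselves censor deaths.** A Kaplan-Meier curve is then the like-for-like comparison, and it can be shown as a supplement.

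**Conclusion.** The concern holds. The plan applies Kaplan-Meier to two primary endpoints without saying how death without brain failure is handled. On the more natural reading, the reported failure rate exceeds the proportion of patients who fail whenever failures follow such deaths. The direction of that bias does not depend on the assumed rates.

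The size does. The ranges above assume constant independent hazards, failure rates that the documents do not give, and medians that are not specific to the enrolled RPA class I and II patients. Confidence is high in the omission and the direction, and much lower in the magnitude. Regional control is where the issue is most likely to matter. The change should be made, but the trial's size and its feasibility criterion do not depend on it.

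**What to change.** In section 13.3:

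- Estimate local failure and regional failure separately by Aalen-Johansen cumulative incidence, with death without that failure as the competing event. Report 95% confidence intervals and numbers at risk at 6 and 12 months.
- For regional failure, state whether follow-up for new lesions continues after a patient leaves the study at local progression. If it ends there, make local progression a further competing event. If it continues, use the later data where available.
- State how hospice discharge is handled, and do not treat it as non-informative censoring without a sensitivity analysis.
- Keep Kaplan-Meier for overall survival and progression-free survival. Show a Kaplan-Meier control curve, labelled as failure in the absence of death, only as a supplement where the published comparator is itself Kaplan-Meier.

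The cost is SAP wording, standard software and two displays for the historical comparison. No new data are needed if local progression is a competing event. Using regional or vital status after a patient leaves the study would require that information to be collected. The sample size does not change.
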